### 11.4 Confirmatory Measurement/Duration of Response

### 11.4.1 Confirmation

To be assigned a status of PR or CR, changes in tumor measurements must be confirmed by repeat assessments that should be performed no sooner than 6 weeks after the criteria for response are first met.

Protocol 2011-0465 ASeptember 6, 2017 Page 47 of 50

#### 11.4.2 Duration of overall response

The duration of overall response is measured from the time measurement criteria are met for CR or PR (whichever is first recorded) until the first date that recurrent or progressive disease is objectively documented (taking as reference for progressive disease the smallest measurements recorded since the treatment started).

The duration of overall CR is measured from the time measurement criteria are first met for CR until the first date that recurrent disease is objectively documented.

#### 11.4.3 Duration of Stable Disease

Stable disease is measured from the start of the treatment until the criteria for progression are met, taking as reference the smallest measurements recorded since the treatment started.

## **12.0 STATISTICAL CONSIDERATIONS**

This is a single arm phase II trial to evaluate safety and efficacy of treatment with pazopanib for 24 weeks in patients with VHL who have measurable VHL related lesions.

12.1 Design and sample size/power

In this study, we will treat up to 40 patients with VHL who have measurable VHL related lesions. Patients will receive Pazopanib 800mg PO daily for up to 24 weeks. Patients may choose to continue the regimen beyond 24 weeks until evidence of objective disease progression. Efficacy will be determined by the RECIST overall response rate (CR+PR) at 24 weeks. Early termination due to progressive disease or toxicity will be considered as a failure. Patients not completing 1 month of therapy due to a reason other than drug toxicity or progressive disease will be considered inevaluable. We will monitor for any lesion progression (PD) and drug discontinuation due to toxicity (DD) during the whole period of the treatment simutaneously. If there is a high probability that the PD rate exceeds 20% or the DD rate exceeds 10%, the trial will be stopped early and the drug will not be considered of interest for further study. Formally, the study will be terminated if Pr(PD Rate > 0.20 | Data) > 0.90 or Pr(DD)Rate > 0.10 | Data) > 0.90. The assumed prior distributions for PD rate and DD rate are Beta (0.2, 0.8) and Beta (0.1, 0.9), respectively, with one patient's worth of information. The study will be monitored in cohorts of 10 patients. Consideration to stop the trial will be given according to the stopping boundaries in Table 1. The operating characteristics for these stopping rules are summarized in Table 2, based on 10,000 simulations. Specifically, if the PD rate is 20% and DD rate is 0.10, then there is a 27% chance to stop the trial early and the average expected number of patients

Protocol 2011-0465 ASeptember 6, 2017 Page 48 of 50

treated will be 33. On the other hand, if (PD rate, DD rate) are (0.10, 0.05), or (0.10, 0.30), then the early stopping probabilities will be 3% and 94% and the average numbers of patients treated are expected at 39 and 16, respectively. If the trial continues to the end with 40 patients treated, we will be able to estimate the response rate at 24 weeks with standard error not larger than 0.08, i.e., the half length of the 95% confidence interval will not exceed 15%.

Total Number of Patients Treated	Stop if number of Progressions >=	Stop if number of Drug Discontinuation (due to Toxicity) >=
10	4	3
20	7	5
30	10	6

Table 1. Stopping boundaries for PD and DD monitoring.

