#### 5.2 Duration of Therapy

In the absence of treatment delays due to adverse event(s), treatment may continue until one of the following criteria applies:

- Disease progression
- Intercurrent illness that prevents further administration of treatment
- Unacceptable adverse event(s)
- Patient decides to withdraw from the study, or
- General or specific changes in the patient's condition render the patient unacceptable for further treatment in the judgment of the investigator.
- 5.3 Duration of Follow Up

Patients will be followed every 3 months for 24 weeks after stopping study drug treatment or until death, whichever occurs first. Patients that have stopped study drug treatments for unacceptable adverse events will be followed until resolution or stabilization of the adverse event. Follow-up will consist of a phone call or medical record review.

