11.3.3 Evaluation of best overall response

The best overall response is the best response recorded from the start of the treatment until disease progression/recurrence (taking as reference for progressive disease the smallest measurements recorded since the treatment started). The patient's best response assignment will depend on the

Protocol 2011-0465 ASeptember 6, 2017 Page 46 of 50

Target Organ Lesions	Non-Target Organ Lesions	New Lesions	Overall Response
CR	CR	No	CR
CR	Incomplete response/SD	No	PR
PR	Non-PD	No	PR
SD	Non-PD	No	SD
PD	Any	Yes or No	PD
Any	PD	Yes or No	PD
Any	Any	Yes	PD

achievement of both measurement and confirmation criteria.

Note:

- X For the purposes of this study, response rate (RR) is based on CR+PR+SD.
- X Patients with a global deterioration of health status requiring discontinuation of treatment without objective evidence of disease progression at that time should be classified as having "symptomatic deterioration." Every effort should be made to document the objective progression, even after discontinuation of treatment.
- X In some circumstances, it may be difficult to distinguish residual disease from normal tissue. When the evaluation of complete response depends on this determination, it is recommended that the residual lesion be investigated (fine needle aspirate/biopsy) before confirming the complete response status.

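### Treating month-1 leavers as inevaluable can only raise the 24-week CR+PR rate, and later leavers for other reasons have no stated classification

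*Combined protocol and SAP*

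**What the plan says.** All the rules are in section 12.1 of the combined protocol and SAP.

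- Size: "In this study, we will treat up to 40 patients with VHL who have measurable VHL related lesions". Replacement of inevaluable patients is not described.
- Endpoint: "Efficacy will be determined by the RECIST overall response rate (CR+PR) at 24 weeks".
- Leavers counted against the drug: "Early termination due to progressive disease or toxicity will be considered as a failure".
- Leavers removed: "Patients not completing 1 month of therapy due to a reason other than drug toxicity or progressive disease will be considered inevaluable".
- Precision: if 40 patients are treated, the response rate is to have a "standard error not larger than 0.08" and a 95% half-length of at most 15%.
- Monitoring: the stopping boundaries (Table 1 of section 12.1) are indexed by "Total Number of Patients Treated".

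Section 5.2 lists reasons for stopping that are neither progression nor toxicity: intercurrent illness, a change in condition in the investigator's judgment, and "Patient decides to withdraw from the study, or" in the patient's own decision. Section 12.1 does not say how a patient counts who stops for one of these after 1 month but before week 24. Section 12.2 plans 95% posterior credible intervals, but names no analysis set and no prior for the response rate.

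**The concern.** The trial has one arm and no concurrent control, so the response rate is read at face value and its denominator matters directly. A rule that removes only patients who could not have become responders moves the estimate one way. A second group, the later leavers for other reasons, has no assigned outcome. Section 10.1 makes the principal investigator the final arbiter of response, so their handling could be settled after the results are known. The precision statement is written for 40 patients, while the exclusion rule allows fewer to enter the estimate.

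**Working it through.** **Inputs.** From section 12.1: up to 40 treated, CR+PR at 24 weeks, standard error at most 0.08, half-length at most 15%. From section 7.2.1: first response scan at the end of cycle 3, i.e. week 12. From section 11.4.1: PR or CR confirmed no sooner than 6 weeks after the criteria are first met. Assumed, because the documents give no figure: k = 2, 4 or 8 patients removed (5%, 10% or 20% of 40), and 12 responders among the 40 treated (30%).

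**Step 1: the stated precision.** The standard error is largest at p = 0.5, where SE = sqrt(0.25/n). At n = 40 it is sqrt(0.25/40) = 0.0791, which meets 0.08. The half-length at p = 0.5 and n = 40 depends on the interval:

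- 1.96 x 0.0791 = 15.5%
- Wilson interval: 14.8%
- credible interval with a uniform prior: 14.9%

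So the standard error reproduces. The 15% reproduces with Wilson or a uniform-prior credible interval, but not with 1.96 x SE.

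**Step 2: can a month-1 leaver be a responder?** The sequence is exit before about week 4, first scheduled scan at week 12, confirmation at least 6 weeks after criteria are met. Section 7.2.2 does ask for imaging at early withdrawal. A response would therefore have to appear within the first month and be confirmed off drug, and section 5.3 limits follow-up to phone calls or record review. In practice the number of responders in this group is zero.

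**Step 3: effect on the rate.** With R responders among 40 and k non-responders removed, the reported rate is R/(40-k), which is R/40 multiplied by 40/(40-k).

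| k removed (assumed) | Factor | Rate if 12 of 40 respond |
|---|---|---|
| 0 | 1.00 | 12/40 = 30.0% |
| 2 | 1.05 | 12/38 = 31.6% |
| 4 | 1.11 | 12/36 = 33.3% |
| 8 | 1.25 | 12/32 = 37.5% |

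For later leavers there are two readings. If four month-1 leavers are removed and four later non-responding leavers count as non-responders, the rate is 12/36 = 33.3%. If all eight are removed, it is 12/32 = 37.5%.

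**Step 4: effect on precision at p = 0.5.**

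| n in the estimate | SE | 1.96 x SE |
|---|---|---|
| 40 | 0.0791 | 15.5% |
| 39 | 0.0801 | 15.7% |
| 36 | 0.0833 | 16.3% |
| 32 | 0.0884 | 17.3% |

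SE of at most 0.08 needs n of at least 0.25/0.08^2 = 39.06, i.e. 40 patients, so one exclusion passes the bound, by 0.0001. Away from p = 0.5 there is room: at n = 36 the bound holds for p up to 0.36, and at p = 0.30 the SE is sqrt(0.21/36) = 0.076.

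**The case against.** The strongest case against runs as follows. The rule is prespecified and visible, and it already counts progression and toxicity exits as failures. The response rate carries no null value or decision threshold; the only formal rules use progression and drug discontinuation. The dropout counts are assumptions, and with one exclusion the change is small (12/39 = 30.8% against 30.0%). All of this stands, and it limits the size and consequence of the point. It does not change the direction of the bias or supply the missing rule for later leavers.

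Three stronger readings are tempting, and the documents do not support them.

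- *That exclusions break the stated precision.* The statement is conditional on 40 treated and is a worst-case bound. The 1.96 x SE half-length is 15.5% before anyone is excluded, so that shortfall is not caused by exclusions; four exclusions add about 0.8 points. The response figures cited in the background (30% for pazopanib in advanced renal cell carcinoma, 6 of 18 renal lesions with sunitinib) lie where the SE bound still holds at n = 36.
- *That later leavers bias the rate.* The plan is silent on them. If they count as non-responders there is no inflation, so this is an ambiguity and not a shown bias. Section 7.2.2 asks for a response assessment at the end of treatment and section 11.3.3 has a best-response table, but neither is tied to the 24-week rate.
- *That excluding patients dilutes the progression and discontinuation monitoring.* Excluding them cannot dilute a rate. Only keeping inevaluable patients in the Table 1 count could, and the plan does not say whether they are kept.

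Nor do the documents show how often month-1 withdrawal for other reasons reflects tolerability. The argument does not need that, because it rests on the timing of scans and confirmation.

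**Conclusion.** The point holds in a limited form. Removing month-1 leavers can only raise the 24-week CR+PR rate, by 40/(40-k): from 30% to 31.6%, 33.3% or 37.5% for k of 2, 4 or 8. This rests on assumed values of k and of the response rate, on 40 patients being treated, and on the section 12.1 endpoint. Section 11.3.3 says "response rate (RR) is based on CR+PR+SD", which is a different quantity and must be reconciled separately. Later leavers for other reasons are an open classification that adds to the inflation only if they are dropped. The loss of precision is slight and matters only near a 50% response rate. Because a stated rule builds in a one-directional error in the efficacy estimate of an uncontrolled trial, and the repair is simple, the change should be made.

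**What to change.** In sections 12.1 and 12.2:

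1. Define the primary efficacy set as all patients who receive at least one dose of pazopanib.
2. Count anyone without a qualifying 24-week response as a non-responder, whatever the reason for leaving and whenever it happens. This replaces the inevaluable rule and closes the gap after 1 month.
3. Report the evaluable-only rate as a sensitivity analysis, with the number excluded and the reasons.
4. Restate the precision with the interval method and prior to be used. With all 40 counted, the worst-case SE stays at 0.0791 whatever the dropout.
5. Say in one sentence whether patients now called inevaluable count toward the 10, 20 and 30 in Table 1.

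The cost is a change of wording. No extra patients or assessments are needed. The reported response rate may be slightly less favourable.

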Pazopanib C24 at steady-state was greater than 15  $\mu$ g/mL in 93% of subjects who received 800 mg once daily in Study VEG10003. Individual subjects receiving pazopanib doses below 800 mg once daily can achieve plasma concentrations over 15  $\mu$ g/mL, albeit at a lower frequency compared with what is observed at 800 mg once daily. Therefore, the pharmacokinetic and pharmacodynamic results across clinical studies demonstrate that pazopanib 800 mg once daily results in plasma concentrations that provide optimal biologic effects associated with VEGFR inhibition in the greatest proportion of subjects.

Additional support for an 800 mg once daily pazopanib dose comes in results from Study VEG105192, a 435-subject Phase III study of pazopanib (800 mg once daily) versus placebo in treatment-naïve and cytokine-pretreated subjects with renal cell carcinoma (RCC). In this study, the median progression-free survival (PFS) in the pazopanib arm was 9.2 months (95% CI, 7.4, 12.9) compared to 4.2 months (95% CI, 2.8, 4.2) in the placebo arm. This finding represented a statistically significant improvement in PFS in response to pazopanib monotherapy (HR 0.46, 95% CI 0.34 to 0.62, p<0.0000001). In addition, the response rate (defined as the percentage of subjects achieving either a confirmed complete or partial response according to RECIST) in the pazopanib arm was 30% versus 3% in the placebo arm, and the median duration of response in pazopanib-treated subjects was 58.7 weeks. Results from Study VEG105192 therefore clearly indicate that an 800 mg once daily dose of pazopanib is highly effective in treating subjects with advanced RCC.

Clinical data from more than 20 clinical Phase I, II, and III studies are available. As of the cutoff date, 09 September 2008, approximately 1600 subjects with cancer have received pazopanib in clinical studies conducted by Novartis Pharmaceuticals or NCI. Clinical data indicate that (a) pazopanib is absorbed after oral administration, (b) the 800 mg daily dosing regimen is an active monotherapy dose for subjects with cancer, providing optimal biologic and clinical effects associated with VEGFR inhibition, (c)

Protocol 2011-0465 ASeptember 6, 2017 Page 8 of 50

pazopanib is generally well-tolerated at the 800 mg daily dosing regimen, and (d) pazopanib has encouraging efficacy in specific tumor settings such as RCC, sarcoma, NSCLC, cervical and ovarian cancer.

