## Table 1. Best Response of von Hippel-Lindau Lesions by RECIST after Sunitinib

Abbreviations: RECIST, Response Evaluation Criteria in Solid Tumors; NET, neuroendocrine tumors.

Of the 21 evaluable individual HB lesions, there were no partial responses (PR). In comparison, 6 of 18 RCC lesions responded with a PR, (P=0.014). All five pancreatic NETs responded with SD. None of the seven retinal angiomas demonstrated any shrinkage on ophthalmoscopy; however, two patients with retinal angiomas complained of increased hyperemia and eye discomfort during sunitinib treatment. When change in

Protocol 2011-0465 ASeptember 6, 2017 Page 10 of 50

lesion size was evaluated as a percentage by organ site per individual, RCC decreased a mean of 14.4% by the end of cycle four, NETs a mean 12.7%, and HB, 5.9% (Table 2). When size change was assessed as a continuous variable, both RCCs and NETs showed significant size decrease after four cycles of sunitinib therapy.

Forty-eight–week follow-up scans were obtained for renal lesions in five patients. In these patients, who had been finished with therapy for 6 months, RCC and NETs had regrown to close to baseline measurements but no larger (Table 2).

		Mean (Standard Error)						
	Baseline	Cycle 2	Percent	Cycle 4	Percent	Week 48	Percent	
Tumor Type	Size(cm)	Size (cm)	Change	Size (cm)	change	Size (cm)	change	
					-14.42		-3.37	
Renal Cell Carcinoma	2.41 (0.21)	2.04 (0.21)	-16.41 (3.9)	2.06 (0.22)	(4.5)	2.34 (0.24)	(5.7)	
P value		0.0004		0.0035		0.6098		
					-12.69		-1.72	
Pancreas NET	1.89 (0.28)	1.81 (0.28)	-3.59 (3.7)	1.64 (0.28)	(4.0)	1.89 (0.29)	(5.2)	
P value		0.284		0.011		0.959		
Hemangioblastoma	0.81 (0.08)	0.81 (0.08)	0.65 (3.4)	0.76 (0.08)	-5.9 (5.4)	0.76 (0.09)	-6.2 (5.4)	
P value		0.8	350	0.2	80	0.32	0	

Table 2. Mean Change from Baseline in Size of von Hippel-Lindau Lesions after Treatment with Sunitinib.	Table 2. Mean Change	e from Baseline	n Size of von	Hippel-Lindau	Lesions after	Treatment with Sunitinib.
---	----------------------	-----------------	---------------	---------------	---------------	---------------------------

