#### 2.4 Rationale for Current Study:

In our previous study we found that sunitinib, an oral small-molecule inhibitor of VEGFR, PDGFR, Flt3, and cKit, provides a consistent response in RCCs but not in CNS hemangioblastomas from patients with VHL. Endothelial VEGFR and FGFR are expressed differently in RCCs and HBs. Based on these observations, we would like to further expand our observations in VHL patients with measurable VHL lesions. We predict that pazopanib, an orally bioavailable small molecule inhibitor of VEGFR as well as other receptor tyrosine kinases, will provide at least the same benefit as sunitinib in a broad VHL patient population, but may provide superior overall quality of life. Phase III studies and MD Anderson Cancer Center clinical experience with pazopanib suggests that this agent may result in fewer toxicities when compared with sunitinib. As individuals with VHL need to balance the impact of disease progression on their overall outlook with the possible consequences of being on chronic therapy which produces continuous side effects, pazopanib may be an acceptable choice. In addition, although our initial clinical and tissue based observations suggest that sunitinib did not provide any clear shrinkage of hemangioblastomas in our clinical study, these observations require further validation. For this reason, we have chosen to proceed with a larger single arm study evaluating pazopanib in the treatment of patients with VHL, but will not exclude individuals with hemangioblastomas, nor will we make it a requirement for individuals who enroll on this study to have RCC.

Protocol 2011-0465 ASeptember 6, 2017 Page 13 of 50

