### 12.2 Analysis Plans

If the trial is stopped early, this drug will not be considered of interest for future study VHL patients. If all 40 patients are accrued, we will estimate the response rate, early progression rate, toxicity rate and their corresponding 95% posterior credible intervals.

Biomarker endpoints and genetic mutations will be measured at baseline and/or over time. Summary statistics, including frequency tabulation, means, standard deviations, median, and range, will be used to describe subject characteristics and marker data. The chi-squared ( $\gamma^2$ ) test or Fisher's exact test will be used to test the association between two categorical variables, such as response and prognostic factors and discrete markers. The association among various continuous and discrete markers and response may be assessed first by the exploratory data analysis graphically and tested using Wilcoxon rank sum test. Correlation among continuous biomarkers will be examined by Pearson or Spearman rank correlation coefficients. Both univariate and multivariate logistic regressions may be performed to model the baseline prognostic factors such as age, gender, race, smoking history, performance status, markers, etc, on response, when appropriate. We will also use the generalized estimating equations to model correlated discrete variables. Repeated measures analysis including mixed effects model will be performed to analyze continuous biomarkers change over time. Time to progression (TTP) will be estimated using the Kaplan-Meier method. Log-rank test will be performed to test the difference in survival between prognostic groups. Regression analyses of survival data based on the Cox proportional hazards model will be

Protocol 2011-0465 ASeptember 6, 2017 Page 49 of 50

conducted on TTP. The proportional hazards assumption will be evaluated graphically and analytically, and regression diagnostics (e.g., martingale and Shoenfeld residuals) will be examined to ensure that the models are appropriate.

Table 2. Operating characteristics for the stopping rules for excessive PD rate or DD rate

True PD Rate	True DD Rate	Probability of	Average Expected #
		Early	of Patients
		Termination	
0.10	0.05	0.03	39.2
0.30	0.05	0.57	25.8
0.20	0.10	0.27	33.1
0.30	0.10	0.61	24.6
0.30	0.15	0.71	22.1
0.10	0.20	0.64	25.7
0.20	0.20	0.70	23.4
0.30	0.20	0.84	18.9
0.10	0.30	0.94	16.3

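### With 40 evaluable patients, the standard-error bound of 0.08 implies a 95% confidence-interval half-length of up to 15.5%, so the stated 15% ceiling is slightly too low.

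*Combined protocol and SAP*

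**What the plan says.** Section 12.1 plans a single arm in which "we will treat up to 40 patients with VHL who have measurable VHL related lesions". The efficacy measure is binary: "Efficacy will be determined by the RECIST overall response rate (CR+PR) at 24 weeks". The section gives no response-rate hypothesis and no power figure for that measure. What it offers is a precision statement, introduced by "If the trial continues to the end with 40 patients treated": the standard error is bounded at 0.08, and this bound is re-expressed through an i.e. as "the half length of the 95% confidence interval will not exceed 15" per cent. No interval method and no assumed response rate are named.

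Two other statements bear on it. Section 12.1 classes as inevaluable those patients who stop within the first month for a reason other than toxicity or progression. Section 12.2 describes a different kind of interval for the final report: "we will estimate the response rate, early progression rate, toxicity rate and their corresponding 95% posterior credible intervals". It names no prior for the response rate.

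**The concern.** The i.e. presents the standard-error bound and the half-length bound as the same fact. They are not: multiplying 0.08, or the exact maximum behind it, by 1.96 gives more than 15%. Both bounds are worded as limits that hold whatever the response rate turns out to be, so they have to hold at the worst case, a rate of 50%.

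Little is at stake beyond accuracy. But this sentence is the only place where the plan says what 40 patients will deliver on efficacy, so a hard limit there should be true as written.

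**Working it through.** **Inputs.** n = 40, the standard-error ceiling of 0.08, the half-length ceiling of 15% and the 95% level all come from section 12.1. The worst case p = 0.5 is my reading of the bound wording, since no response rate is assumed. The normal quantile is 1.96.

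**Step 1: the plan's standard error.** SE = sqrt(p(1-p)/n), largest at p = 0.5: sqrt(0.25/40) = 0.0791. This is below 0.08, so the first bound is reproduced.

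**Step 2: the plan's half-length.** Half-length = 1.96 x SE.
- From the exact maximum: 1.96 x 0.07906 = 0.15495, or 15.5%.
- From the stated ceiling: 1.96 x 0.08 = 0.1568, or 15.7%.

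Neither gives a 15% ceiling, so the second bound is not reproduced.

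**Step 3: what 15% would require.** SE would have to be at most 0.15/1.96 = 0.0765. At p = 0.5 that needs 1.96^2 x 0.25/0.15^2 = 42.7, so 43 patients; 42 give 15.1% and 43 give 14.9%.

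**Step 4: where the ceiling fails.** Half-length by number of responders out of 40, normal approximation:

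| Responders | Half-length |
|---|---|
| 12 | 14.2% |
| 14 | 14.8% |
| 15 | 15.003% |
| 16 | 15.2% |
| 20 | 15.5% |
| 24 | 15.2% |
| 25 | 15.003% |
| 26 | 14.8% |

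The ceiling is exceeded from 15 to 25 responders (37.5% to 62.5%), by a negligible amount at either end.

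**Step 5: other interval methods.** Maximum half-length over all possible counts, n = 40:
- Wilson: 14.8%
- Equal-tailed credible interval, Beta(1,1) prior: 14.9%
- Equal-tailed credible interval, Beta(0.5,0.5) or Beta(0.2,0.8) prior: 15.04%
- Clopper-Pearson: 16.2%

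The priors are assumptions. Beta(0.2,0.8) is the plan's prior for the progression rate, borrowed here only as an example of a prior worth one patient.

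**Step 6: fewer evaluable than treated.** The documents do not say how many patients may become inevaluable, so these counts are illustrative, at p = 0.5:
- 39 evaluable: SE 0.0801, half-length 15.7%
- 38 evaluable: SE 0.0811, half-length 15.9%
- 37 evaluable: SE 0.0822, half-length 16.1%
- 36 evaluable: SE 0.0833, half-length 16.3%

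A single inevaluable patient is enough to take the maximum standard error just past 0.08.

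**The case against.** The strongest defence is rounding. As a whole number, 15.495% is 15%, and section 12.1 rounds in the same way elsewhere: expected sample sizes of 33.1, 39.2 and 16.3 in the operating-characteristics table become 33, 39 and 16 in the text. This very likely explains the figure. It does not make the sentence true, because a value rounded down cannot serve as an upper limit. The same sentence rounds the standard error up, from 0.0791 to 0.08, which is the right direction for a bound.

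A second defence is that other intervals meet 15%, including, for practical purposes, the credible interval planned in 12.2. That stands as a limit on the point. It does not rescue the wording, because 12.1 obtains the half-length directly from the standard error, which is the normal approximation, and names no other method.

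A third is that the response rates cited in the documents are lower than those where the excess arises. Section 2.2 reports a response rate that "in the pazopanib arm was 30% versus 3% in the placebo arm" in advanced renal cell carcinoma, which gives 14.2%. In the sunitinib data of section 2.3.1, "6 of 18 RCC lesions responded with a PR", which gives 14.6%. These are indirect: the second counts lesions rather than patients, and section 2.4 says of eligibility "nor will we make it a requirement for individuals who enroll on this study to have RCC". They support a low severity, but a bound stated without an assumed rate still has to hold at every rate.

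A reader might go further and infer that no 95% interval can meet 15% with 40 patients, or that the trial needs 43. The documents support neither. Step 5 shows intervals that stay below 15%, and nothing in 12.1 derives the 40 from a 15% target.

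**Conclusion.** The 15% ceiling is wrong as written, by at most 0.5 percentage points. With 40 evaluable patients the standard-error bound holds at 0.0791, but the normal-approximation half-length it implies reaches 15.5% and is above 15% for 15 to 25 responders. This rests on two readings: that the i.e. denotes the normal approximation, and that an unconditional bound must hold at a 50% response rate.

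Severity is minor. The sample size, stopping boundaries and operating characteristics do not use the figure and are unaffected. Separately, both bounds in the sentence are tied to patients treated, whereas they hold as computed only if all 40 are evaluable.

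**What to change.** In 12.1, replace the 15% ceiling with: *will not exceed 15.5% (normal approximation, 40 evaluable patients, maximum at a 50% response rate)*. State the standard-error bound for 40 evaluable patients as well, since 12.1 itself provides for inevaluable ones.

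Optionally, describe the credible interval of 12.2 here instead, with its prior named in both sections and its maximum half-length given for that prior (14.9% with Beta(1,1), 15.04% with Beta(0.5,0.5), each for 40 evaluable patients). This would make the two sections describe one interval, but it requires choosing a response-rate prior, which is a separate decision and is not needed to correct the arithmetic.

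The cost is one sentence. The stated precision looks slightly less favourable, and nothing in the design changes.
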